1.3. Benefit/Risk Assessment

Considering the significant unmet need for safe and effective, orally administered treatments for UC, etrasimod may potentially provide therapeutic benefit via S1P receptor modulation.

Adverse events that have been reported with S1P receptor modulators include bradycardia at the first dose or atrioventricular (AV) block, macular edema, hypertension, headache, cough, dyspnea, back pain, influenza, and diarrhea.

Safety and tolerability of etrasimod has been evaluated in Phase 1 studies with healthy adult participants at single doses up to 5 mg and repeat doses up to 4 mg once daily. Repeated doses of 2 mg have been evaluated in Phase 2 studies of participants with moderately to severely active UC (refer to the current edition of the IB). Etrasimod was found to be safe and well tolerated in these studies, with no clinically significant safety concerns with respect to vital signs, electrocardiograms (ECGs), pulmonary function tests (PFTs), ophthalmoscopy, or clinical laboratory tests. Etrasimod produced a dose-dependent sustained decrease in total lymphocyte count, which is expected given etrasimod's mechanism of action. Lymphocyte counts were within normal limits by 7 days after the last dose.

A Japanese/Caucasian ethnobridging pharmacokinetic (PK) and pharmacodynamic (PD) study (Study APD334-109) was conducted that demonstrated etrasimod 1 mg and 2 mg once-daily dosing regimens were safe and generally well tolerated by both Japanese and Caucasian participants. In that study, single and multiple dose etrasimod (1 mg and 2 mg) mean exposure (maximum observed plasma or serum concentration [C_{max}] and area under the plasma concentration-time curve [AUC]) were slightly to moderately higher in Japanese participants compared to Caucasian participants, but this was attributable to differences in body weight rather than ethnicity. No differences were observed in absolute lymphocyte counts (ALCs) between Japanese and Caucasian participants following multiple dose administration of etrasimod and levels returned to near baseline during the 7-day washout period. Additionally, there were no clinically relevant first-dose heart rate (HR) differences.

Detailed information regarding the known and expected benefits and risks and reasonably expected adverse events of etrasimod can be found in the IB, which serves as the single reference safety document for this study.

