10.4. Missing Data

Participants with a lack of efficacy adverse event related will be considered as having a treatment nonresponse outcome in the analysis of all endpoints, including the primary endpoint. In addition,

participants who initiate an agent not allowed in combination with the study treatment that can affect the efficacy of the study treatment, such as an immunosuppressant or corticosteroid, or who have an increase in dose over baseline levels for treatment of worsening disease symptoms will be considered nonresponders for binary responder-type endpoints thereafter or be handled by per protocol analysis.

Participants discussed above will be considered as having a known outcome at the analysis timepoint (ie, a treatment failure outcome) and not as having missing data. Participants who discontinue the double-blind study for reasons other than a lack of efficacy adverse event related to UC will be considered as having missing data and will be handled in the primary and sensitivity analyses as follows.

A full description of the handling of missing data will be provided in the SAP.

Primary method of handling missing data

In the primary analysis of the primary endpoint and main analyses of all binary responder-type endpoints, missing data, eg, component scores of MMS at the planned assessment timepoint, will be imputed using multiple imputation methodology (Rubin 1987) under the missing at random (MAR) assumption. Binary responder-type endpoints will subsequently be computed from observed and imputed data and analyzed using methods as outlined in Section 10.12.1.

In the main analysis of continuous or score endpoints, such as changes from baseline in MMS subscores, biomarker measures, urgency numeric rating scale (NRS), abdominal pain NRS, and health-related quality of life measures, missing data will be handled using the same multiple imputation methodology above and analyzed by either analysis of covariance or a mixed-effect model with repeated measures. Detailed methods will be provided in the SAP.

Sensitivity analyses for missing data

Sensitivity analyses will be performed as follows.

- All participants with missing data, regardless of reason for missingness, will be considered as nonresponders for binary responder-type endpoints.

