# 6.4. Windowing Conventions

All scheduled study visits are defined relative to Study Day 1, the date of first dose administration. Scheduled visit windows are defined in Clinical Study Protocol APD334-203 Appendix 1. A windowing convention will be used to determine the analysis visit value for a given measurement and will be applicable for all by-visit summaries and analyses for efficacy and safety data. Refer to Table 2 for specific visit windows.

For cardiac remonitoring upon treatment reinitiation after Day 2, as evidenced by more than 1 timed measurement in vital signs or electrocardiogram (ECG) parameters on the same collection date of an unscheduled visit, measurements will be mapped to analysis visit of Cardiac Remonitoring 1, Cardiac Remonitoring 2, etc. in the respective analysis dataset. For analysis, each timed measurement will be programmatically assigned to the nearest hourly timepoint (eg, Predose, 1-hour Postdose) based on their relationship to the dosing time on the same day. If the dosing date/time on the same day is missing, the timepoint will remain missing. Once mapped, these timed measurements from cardiac remonitoring visits will not be considered for any other analysis visit.

Windowing will be applied prior to any missing data calculations. The last non-missing measurement taken prior to Day 1 (including unscheduled assessments) will be labeled as "Baseline". Unless stated otherwise, data from all visits including scheduled, unscheduled and ET visits will be eligible for allocation to an analysis visit. The 2-Week and 4-Week Follow-Up visits will not be included in the visit windows and will be summarized separately without any window applied.

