If one or more results for a variable are assigned to the same analysis visit, the result with the date closest to the protocol scheduled day will be used in the analysis, except for component subscores of MMS or TMS, in which case, the composite score and component subscores from the same date will be used in the analysis. If two measurements in the same analysis visit window are equidistant from the protocol scheduled study day, the earliest measurement will be used in the analysis. If multiple assessments are available on the same day, then the average of the assessment will be used in the analysis, except for laboratory and ECG data where the assessment at the earliest time of the same day will be used. If both central and local assessments of the same ECG or lab test are available on the same day/analysis visit, the central result will take precedence over the local result.

Document: \quintiles.net\enterprise\Apps\sasdata\SASb\SAS\Arena\APD334\RZA28116\Biostatistics\Documenta

tion\SAP\503-Final SAP v2.0\APD334-203\_SAP\_Final v2.0-20231120\_clean.docx

Author: PPD Version Number: 2.0

Version Date: 20Nov2023

Template No.: CS\_TP\_BS016 Revision 7 Reference: CS\_WI\_BS005

Effective Date: 01Nov2021

Page 23 of 70

For the overlapping visit windows at Week 12 and Week 8, a hierarchical algorithm will be applied as following: always map to the Week 12 study visit if the study day falls within the visit window of the Week 12 study visit, then assess the other records for the Week 8 study visit.

Table 2: Visit Windows for Efficacy and Safety Analyses

For All Efficacy (Except Endoscopy/MMS/Histology), Efficacy-Related Biomarkers, Safety Labs and Vital Signs			
Scheduled Study Visit (Protocol Scheduled Day)	Analysis Visit Window (Study Day)		
Baseline	≤1		
Week 0 (Day 1)	1		
Week 0 (Day 2)a	2		
Week 2 (Day 15 ± 3)	2 to 22, or 3 to 22a		
Week 4 (Day 29 ± 3)	23 to 43		
Week 8 (Day 57 ± 3)	44 to 71		
Week 12 (Day 85 ± 7)	> 71		
	gy/All Composite Endpoints That Include an Endoscopy Component sysician's Global Assessment, Health-Related Quality of Life, ECGs, OCT,		
Scheduled Study Visit (Protocol Scheduled Day)	Analysis Visit Window (Study Day)		
Baseline	≤1		
Week 0 (Day 1)	1		
Week 0 (Day 2)a	2		
Week 12 (Day 85 ± 7)b,c	66 to 113e (66 to 141 for assessments impacted by COVID-19 pandemic)d		
	or 57 to 113 f (57 to 141 for assessments impacted by COVID-19 pandemic) e		

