#### 15.1. Derivations

Compliance with study treatment is based on the Drug Accountability eCRF and will be calculated as the total number of tablets taken (total dispensed – total returned) divided by the number of tablets expected during the Treatment Period, expressed as a percentage, refer to calculations below.

The total number of tablets expected is defined as the number of tablets that a subject is expected to have taken between their first and last study treatment administration and is numerically identical to the subject's overall study treatment exposure, since the medication is to be taken once daily. On any site visit day, the medication is to be held and taken at the site, after all predose assessments have been completed. For example, if a subject took their last dose of study treatment on Day 60 and returned to the site on Day 78 to return the study treatment bottle, then the total number of tablets expected would be 60, not 77.

 Total number of tablets expected = (date of last study treatment administration – date of first study treatment administration + 1) (days) × 1 (tablet / day)

For all bottles not returned, it will be assumed that all dispensed tablets were taken. For each subject, if a high percentage (> 25%) of bottles were not returned by a subject, additional analyses may be done where bottles not returned are excluded from the overall compliance calculation for that subject. In such analysis, the date of last dose or the date of last bottle return, whichever is earlier, will be used as the "date of last dose" in the calculation above.

Both scheduled and unscheduled study treatment dispensations will be used in the compliance calculation. Overall compliance calculations will be performed for the 12-Week Treatment Period and will be used in determining inclusion/exclusion of participants in the respective Per Protocol Set.

Other derivations are shown below:

- Time on study (weeks) is calculated as ("Date of Completion/Termination of Study" on the eCRF Page "End of Study" – informed consent date + 1)/7.
- Total subject-years on study is calculated as the sum of duration of time on study (days) across all subjects divided by 365.25.
- Exposure (weeks) is calculated as (end date of study treatment start date of study treatment + 1)/7.

Document: \quintiles.net\enterprise\Apps\sasdata\SASb\SAS\Arena\APD334\RZA28116\Biostatistics\Documenta

tion\SAP\503-Final SAP v2.0\APD334-203 SAP Final v2.0-20231120 clean.docx

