#### 19. PHARMACOKINETIC ANALYSIS

Plasma concentrations of etrasimod will be assessed from samples collected prior to dosing and 4 hours (±15 minutes) post-dose (after 12-lead ECG) on Week 0/Day 1, samples collected prior to dosing (trough; within 60 minutes prior to dosing) at Weeks 2, 4, 8, and 12. Additionally, samples are being collected at 2-Week and 4-Week Safety Follow-up visits (for subjects not enrolling into the OLE study), and if possible, at the time of any SAE or adverse event leading to study treatment discontinuation are being collected. Concentrations below the limit of quantification (BLQ) will be assigned a numerical value of zero for the calculation of descriptive statistics in concentrations (except for geometric mean and geometric %CV) and plotting of concentrations. For geometric mean and geometric %CV, the zero values will be excluded.

The pharmacokineticist will determine the strategy for dealing with data affected by protocol deviations or events which may impact the quality of PK concentration data on a case-by-case basis with input from the Pfizer study physician and Pfizer clinical pharmacologist, as needed. Examples for protocol deviations or events include, but

Document: \\quintiles.net\enterprise\Apps\sasdata\SASb\SAS\Arena\APD334\RZA28116\Biostatistics\Documenta

tion\SAP\503-Final SAP v2.0\APD334-203 SAP Final v2.0-20231120 clean.docx

Author: PPD Version Number: 2.0

Version Date: 20Nov2023

Template No.: CS\_TP\_BS016 Revision 7 Reference: CS\_WI\_BS005

\_\_\_\_\_

Effective Date: 01Nov2021

Page 52 of 70

may not be limited to, vomiting on the day prior to trough sample collection, sample processing errors that lead to inaccurate bioanalytical results, and/or inaccurate dosing prior to PK sampling. In the case of an important protocol deviation or event, the affected PK data collected may be excluded from the summaries, calculation of the average steady state trough plasma concentration ( $C_{trough}$ ) based on available Week 2 to Week 12 trough concentrations ( $C_{trough,ss,W2-W12}$ ), exposure-response analysis, and/or population PK analysis, but will still be reported in the study result listings. The time window of 24 hours ±8 hours after the last dose prior to PK sample is required for inclusion in calculating  $C_{trough,ss,W2-W12}$  and summarizing trough.

Unless otherwise specified, PK summaries will use the Pharmacokinetic Set. Exposure-response analysis will use the Safety Set.

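### SAP 6.4 sets no limit on time since last dose, so late early-termination or unscheduled values can serve as Week 12 biomarker, laboratory and vital-sign results

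*SAP*

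**What the plan says.** SAP 6.4 anchors its windows to the start of treatment: "All scheduled study visits are defined relative to Study Day 1, the date of first dose administration". It then states that "data from all visits including scheduled, unscheduled and ET visits will be eligible for allocation to an analysis visit", and the next sentence makes one exception: "The 2-Week and 4-Week Follow-Up visits will not be included in the visit windows and will be summarized separately".

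Table 2 of the SAP has two sets of windows.
- For non-endoscopic efficacy, efficacy-related biomarkers, safety labs and vital signs, Week 12 is any study day above 71. There is no upper limit.
- For endoscopy, MMS, histology, quality of life and ECG, Week 12 is "66 to 113e (66 to 141 for assessments impacted by COVID-19 pandemic)d" (the trailing letters are footnote marks). OCT and PFT start at Day 57.

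If several results fall in one window, the one closest to the scheduled day (Day 85) is used. SAP Appendix 1 lists Week 12 under the treatment period and gives an ET visit the period of whichever analysis visit it is mapped to.

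Protocol 5.1 asks for the ET visit within 7 days of the last dose. Protocol 5.1, 9.5 and Table 6 (footnote b) also provide for ET visits 2 weeks or more after it, when the 2-Week Follow-Up is dropped, and 4 weeks or more after it, when the 4-Week Follow-Up is generally dropped too. Protocol 1.3 reports: "Lymphocyte counts were within normal limits by 7 days after the last dose".

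The SAP sets a last-dose limit only for PK troughs, in Section 19: "The time window of 24 hours ±8 hours after the last dose prior to PK sample is required for inclusion".

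**The concern.** The Follow-Up exclusion works by visit name, not by time off drug. A late ET visit replaces a Follow-Up visit in the schedule but is treated differently in the analysis: the same off-drug blood sample is kept out of Week 12 under one name and eligible for it under the other.

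This matters most for lymphocytes. They are the pharmacodynamic marker of the drug, they recover quickly after stopping, and SAP 16.4 analyses their change and percent change by visit in an MMRM. An off-drug value used as Week 12 pulls the estimated Week 12 change in an active arm toward zero. Calprotectin, hs-CRP, safety labs and vital signs go through the same windows. If stopping is more common on active drug than on placebo, the dilution is uneven across arms.

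**Working it through.** No figure stated in the plan bears on this point, so the check applies the Table 2 windows to pairs of dates. Let L be the study day of last dose, V the study day of the visit, and G = V − L the days off drug. Table 2 tests V only:
- labs, biomarkers and vital signs: Week 12 if V > 71, for any G
- endoscopy and MMS: Week 12 if 66 ≤ V ≤ 113 (141 if COVID-affected), for any G

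**1. The SAP's own dates.** SAP 15.1 illustrates tablet counting with the case "if a subject took their last dose of study treatment on Day 60 and returned to the site on Day 78". G = 78 − 60 = 18 days. Since 78 > 71 and 66 ≤ 78 ≤ 113, any measurement taken at such a visit, if it is the ET visit, maps to Week 12 under both sets of windows. A visit at Day 60 + 14 = 74 labelled 2-Week Follow-Up would be excluded.

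**2. ET visit held as instructed (G ≤ 7).** Labs reach Week 12 only if L + 7 ≥ 72, so L ≥ 65. Endoscopy reaches it only if L + 7 ≥ 66, so L ≥ 59. In both cases the value is at most 7 days off drug.

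**3. Late ET visit.**

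| G | Earliest L mapping to Week 12, labs | Earliest L mapping to Week 12, endoscopy |
|---|---|---|
| 14 days | 72 − 14 = 58 | 66 − 14 = 52 |
| 28 days | 72 − 28 = 44 | 66 − 28 = 38 |

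Earlier visits are open too: L = 43 with ET 14 days later gives V = 57, which is Week 8 for labs.

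**4. Largest gap allowed.** Endoscopy: 113 − 85 = 28 days for a last dose at Day 85 (141 − 85 = 56 if COVID-affected), and 113 − 60 = 53 for a last dose at Day 60 (141 − 60 = 81). Labs, biomarkers and vital signs: no limit.

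**5. Does the closest-to-Day-85 rule prevent this?** It protects a completer whose regular Week 12 sample was taken near Day 85. It does not protect someone who stopped earlier. Hypothetical: L = 72, ET blood count on Day 74 (G = 2, distance 85 − 74 = 11), unscheduled count on Day 86 (G = 14, distance 86 − 85 = 1). The Day 86 value is chosen.

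**6. Illustrative size for lymphocytes.** Protocol 3.2 gives TEAE-related treatment discontinuation in the earlier Phase 2 study as d = 8.0% (2 mg), 5.8% (1 mg) and 0% (placebo). Assume a true reduction R of 50%, and assume that every such participant contributes a Week 12 value fully back at baseline. The apparent reduction is R × (1 − d): 50 × 0.92 = 46.0% for 2 mg, 50 × 0.942 = 47.1% for 1 mg, placebo unchanged. For R from 40 to 60%, 2 mg reads 40 × 0.92 = 36.8% to 60 × 0.92 = 55.2%. This is a worst case for that group, not an estimate. By step 2, early stoppers with a timely ET visit do not reach Week 12 at all, and the protocol says normal limits, not baseline. Discontinuation for other reasons is not in d.

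**The case against.** The strongest reply is that the SAP never promises on-treatment results. SAP 2.5 lists four intercurrent events that force nonresponse, and stopping drug for a reason unrelated to UC is not among them. SAP 5.3 analyses participants by randomised arm. A reader might infer that late endoscopies corrupt the primary endpoint and should become nonresponse. The documents do not support that: using such an observation fits the estimand as written, and overriding it would change the estimand.

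A reader might also infer a breach of Protocol 10.4, where participants who stop for "reasons other than a lack of efficacy adverse event related to UC will be considered as having missing data". That section deals with scores missing at the planned assessment and does not say that an observed ET score is discarded. SAP 3.3 does declare the move from multiple imputation to non-responder imputation.

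A third inference is that every exposure-response plot mixes on-drug troughs with off-drug outcomes. The by-visit plots need a valid trough from the same visit, so the 24 ± 8 hour rule largely protects them. Only MMS change against the average Week 2 to 12 trough is clearly exposed.

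Nor are the extra blood counts in Protocol 9.5 a clear source of recovered values. They are triggered by an abnormal count at the 4-Week Follow-Up, and SAP 18.3 bars them from summaries if done locally.

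Other limits also stand: the 7-day ET instruction, nonresponse for those who leave the study for lack of efficacy or a UC-related event, and no hypothesis tests after the early stop. The Day 60/78 case is a tablet-count illustration that the SAP does not call an ET visit, and as one it would miss the 7-day instruction.

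None of this closes the gap for labs, biomarkers and vital signs. The protocol itself provides for late ET visits, and the window that receives them has no end.

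**Conclusion.** The point holds in a limited form. SAP 6.4 has no condition on time since last dose, and the Day > 71 window is open-ended, so late ET or unscheduled values can be used as Week 12 for lymphocytes, fecal calprotectin, hs-CRP, safety labs and vital signs. That is inconsistent with the SAP's own exclusion of the Follow-Up visits.

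The number of participants affected cannot be derived from the documents and is probably small. On the assumptions in step 6, dilution of an assumed 50% lymphocyte reduction is at most 4.0 percentage points on 2 mg and 2.9 on 1 mg. The actual effect depends on how many ET visits run late, which the documents do not say.

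For the binary Week 12 endpoints the documents do not show an error. One participant is still worth 1/32 = 3.1 points in an arm of the planned size, and more in the smaller trial that SAP 7 expects. SAP Appendix 5 does not count therapy begun on or after the last dose as rescue, although Protocol Table 6 asks for the ET visit before any new treatment. Knowing how many Week 12 scores were taken late would therefore help the reader.

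**What to change.** Add to SAP 6.4, in substance: *for lymphocytes, fecal calprotectin, hs-CRP, safety laboratory tests and vital signs, an ET or unscheduled value may enter a treatment-period analysis visit only if taken no later than 7 days after the last blinded dose; later values are summarised as post-treatment with the Follow-Up data.* Seven days is the protocol's own ET interval. Because lymphocytes are reported normal by then, a shorter limit could be considered for them.

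Apply the same condition to the MMS value in the plot of MMS change against average Week 2 to 12 trough.

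For the binary Week 12 endpoints, keep the estimand and do not force nonresponse. Report by arm how many Week 12 endoscopy/MMS values were taken more than 7 days after the last dose.

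The cost is one sentence, one date condition in programming and one small table. The downside is that a few Week 12 values drop out of the by-visit summaries and the MMRM.

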### 6.5. Statistical Tests

No statistical test will be conducted. Point estimate with 95% confidence intervals (CI) will be reported.

#### 6.6. Common Calculations

For quantitative measurements:

- Change from Baseline = Test Value at Visit X Baseline Value
- Percent change from Baseline = (Test Value at Visit X Baseline Value) / Baseline Value × 100
- Proportion at Visit X = Number of participants satisfying criteria at Visit X / Total number of participants at Visit X

# 6.7. General Study Information

A general table with summary of study information will be generated, including the date of first participant signed informed consent form (ICF), the last participant visit date and the database lock date. All analyses will be conducted using SAS® (v9.4 or later, SAS Institute Inc., Cary, NC).

